	
Part 2: Expansion Phase
 
Once the Recommended Therapeutic Dose has been determined in Part 1 (a), a minimum of 150 patients will be enrolled in to the Expansion Phase, which is split into 3 periods. For participants taking part in the Dose Finding Phase (Part 1), eligibility criteria will be reassessed prior to entering Part 2 of the trial.
 
1) Baseline visit
 
In a minimum of 50 participants the following will be performed:
 

• Administration of a test dose of RESP301, at the RTD

• Assesses response to RESP301 (incl. recording any AEs, FEV1 pre- and post dose and monitoring methaemoglobin levels pre-, during and post- administration, using fingertip sensor; methaemoglobin level should be <=2% before, <=5% during, and <=3% at 30-60 mins post dose (i.e. if still >3% at 30 mins, check again at 60mins post dose).

 
During the visit participants who satisfactorily tolerate the test dose will then be enrolled into the “dormant period” of the study for 12 months.
 
An independent Data Monitoring Committee will review the data from the 50 participants that received the RTD. Based on the data from these participants, it will be decided whether test doses should be administered to further participants before enrolling them into the Dormant Period.
 
2) Dormant Period
 
Dormant period patients are requested at the baseline visit, and monthly follow-up calls, to inform the study team if they develop exacerbation symptoms indicative of a respiratory infection. There will be no other study procedures or data collection during the “dormant study phase” unless the participant experiences exacerbation symptoms.
 
3) Treatment Period
 
A patient who experiences exacerbation symptoms for at least 24 hours should contact the study team as soon as practicable to allow a study interaction to be undertaken remotely (via video link, if possible), within 72 hours of onset of at least one of the following: fever (<math>>38.0^{\circ}\text{C}</math>), systemic malaise, increased cough or wheeze, increased sputum volume or increased purulence. During the remote visit the patient’s symptoms will be discussed and if

--	--

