	
To be evaluated on the full cohort, and separately in the sub-cohort of those who test positive for SARS-CoV-2:
 

• Safety and tolerability of RESP301 in terms of:

○ % of participants able to tolerate the test dose in Parts 1(a), 1 (b) and 2

○ Total counts and cumulative incidence of:

▪ Adverse Events (AEs)

▪ Serious Adverse Events (SAEs)

▪ Suspected Unexpected Serious Adverse Reactions (SUSARs)

▪ Severe AEs

▪ Treatment-related AEs/SAEs

• Feasibility in terms of percentage of patients who, having experienced and correctly reported an exacerbation, receive the treatment within 48 hours of reporting their exacerbation

• Efficacy of RESP301 in terms of:

○ % of participants recovered by Day 7 and Day 14 post starting treatment

○ time to recovery (days until patient feels all their symptoms are back to their usual baseline (all VAS = 0))

○ preventing exacerbation-related hospitalisation and/or death

○ change in CCQ score

Duration of participation in the study	The overall study duration for each participant will be at most approximately 60 weeks, including one or more visits at a study centre in Parts 1/2, monthly follow-up calls, and, for those who experience an exacerbation, one week of treatment and additional monitoring calls at the beginning, during and following the treatment period.
Study population	Participants will be adult patients with spirometry-confirmed COPD or computerised tomography (CT) proven bronchiectasis, recruited from secondary and primary care sites in the UK.
Sample size	
Part 1(a):
 
We aim to recruit up to 48 participants. All participants who complete Part 1a, will also be eligible to enter Part 2 of the trial.
 
Part 1(b):
 
We aim to recruit 8 participants who are not experiencing an exacerbation. These participants will receive a short acting

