### **8.1.7 The Clinical COPD Questionnaire (CCQ) (Part 2 only)**

The Clinical COPD Questionnaire (CCQ) is a validated, self-administered 10-item questionnaire which measures health status and can be used to assess health-related quality of life (van der Molen et al, 2003). It has three domains: symptoms (4 items), functional status (4 items) and mental state (2 items), graded on a 7-point Likert scale from 0 to 6 (0 = no impairment). The final score is the sum of all items divided by 10; separate scores for all three domains can be calculated. Higher scores indicate a worse health status.

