### **10.4.1 General Considerations**

Data will be presented using appropriate summary statistics and patient data listings. In general, missing values will not be replaced unless otherwise stated. Baseline will be considered the latest assessment before first dose of study treatment.

A flow diagram of participant progress will be provided, including the number assessed for eligibility and reasons for exclusion, number enrolled, and participants with early withdrawal from the study, together with the primary reasons for discontinuations. Any recorded protocol deviations will be listed.

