**Table 3: Schedule of Study Assessments (Part 2)**

Procedure	Screen 1	Screen 2/ Baseline Visit 	Dormant Period (monthly calls)	Pre-Treatment call (within 24-72 hrs of exacerbation onset)	Treatment Period (daily monitoring calls for 8 days)	Post Treatment Follow-up call (Day $14\pm 3$ PEoT)	Post Treatment Follow-up call (Day $28\pm 3$ PEoT)	Early withdrawal (Days 0, 14 or 28 $\pm$ 3)
Informed Consent	X	X						
Inclusion and Exclusion Criteria	X	X						
Demographics	X							
Medical History	X			X	X	X	X	X
Medication history and concomitant medications	X	X		X	X	X	X	X
Height, Weight and BMI	X							
Physical Examination 	X	X						
Pulmonary function test 	X	X						
Vital signs	X	X						
Methemoglobin level	X	X						
RESP301 administration 		X			X			
CCQ		X	X		X 	X		
Instructions of nebulizer		X		X	X			
Follow-up 			X					
Review of symptoms				X	X	X		
AE/SAE review	X	X			X	X	X	X
VAS 					X	X		

Body temperature 				X	X	X		
Treatment compliance					X			

 Patients who received a RTD test dose only and did not proceed to the dormant period, will receive a follow-up call on day 7±3 to discuss and record AEs.

 Only done if deemed necessary by the investigator

 Only done in patients who received a RTD test dose at the Baseline visit

 At baseline a single RTD dose for patients who were assigned to test dose and at the treatment period TID for 1- 7 days in patient with an exacerbation

 Done at Day 1 and Day 7

 Patients reminded to contact the study team if they experience exacerbation symptoms

 Daily during the treatment period, and if not recovered by end of treatment, continued until recovery or Day 14 post end of treatment

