## **5. METHODS OF ANALYSIS AND PRESENTATION**

### **5.1 General Principles**

The statistical analysis will be performed using the validated software package SAS version 9.4 or higher (SAS Institute Inc., Cary, NC 27513, USA).

All recorded and derived variables will be presented by treatment group and visits (if appropriate) using descriptive summary tables (continuous data: sample size, mean, standard deviation (SD), minimum, median, maximum; categorical data: sample size, absolute and relative frequency).

The mean and median will be presented to one more decimal place than the raw data. The SD will be presented to two more decimal places than the raw data. The percentages will be presented to 1 decimal place. In all the summaries, the treatment groups will be displayed in the following order: part 1 (RESP301 1 ml, 2 ml, ...6 ml, RESP+Vent 6 ml) and then part 2.

For all parameters, baseline is defined as the last available pre-treatment value (i.e. the last non-missing value available before study drug administration. In general, missing data will be treated as missing and no attempts will be made to impute values for missing data.

No formal interim efficacy analyses are planned in this study; however, several safety interim analyses by the Safety Advisory Committee (SAC) will be performed as detailed in the protocol, see section 7.7 for part 1 and an Independent Data Monitoring Committee (IDMC) will review the safety data on an ongoing basis as described in the DMC charter, see section 10.6 of the protocol.

Subjects who did not receive any study medication (screening failures) will be listed separately and not presented in any table or figure, except in the patient's disposition table.

The versions of the following international dictionaries (MedDRA version 26.1 and WHO DD, version 2024) will be used for medical coding:

Adverse events: Medical Dictionary for Regulatory Activities (MedDRA).

Medical Histories: Medical Dictionary for Regulatory Activities (MedDRA).

Medications: World Health Organization (WHO) Drug Dictionary including Anatomical Therapeutic and Chemical (ATC) classification.

If a medication in the drug dictionary (DD) table is associated with more than one ATC code, the first ATC code will be assigned to that medication.

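### One pre-treatment baseline for all parameters can give test-dosed and untested Part 2 patients different reference points for CCQ change

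*SAP*

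**What the plan says.** **Baseline rule.** Protocol 10.4.1: "Baseline will be considered the latest assessment before first dose of study treatment". SAP 5.1: "For all parameters, baseline is defined as the last available pre-treatment value", explained as "the last non-missing value available before study drug administration". The SAP sentence does not contain the word first and names no period. SAP 5.5 and 5.8, however, tie baseline to the first administration of study medication. Neither document shows a separate baseline for the treatment period.

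**The test dose is study drug.** SAP Table 3 lists it under RESP301 administration: "At baseline a single RTD dose for patients who were assigned to test dose". Protocol 7.4 says the first dose of study intervention is given under clinical supervision. At least the first 50 Part 2 patients receive it. The remainder may go untested if the data monitoring committee agrees (SAP 4).

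**The endpoint.** The protocol synopsis lists "change in CCQ score" as a secondary efficacy endpoint: "To be evaluated on the full cohort, and separately in the sub-cohort of those who test positive for SARS-CoV-2". Protocol 8.1.7 gives the direction ("Higher scores indicate a worse health status") and restricts CCQ to Part 2.

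**CCQ timing.** CCQ is scheduled at the baseline visit, on treatment Days 1 and 7, and at the Day 14 follow-up. SAP Table 3 also marks it in the dormant-period column, whereas the protocol synopsis says: "There will be no other study procedures or data collection during the" dormant phase unless symptoms occur.

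**Grouping.** SAP Table 1 makes all of Part 2 one treatment group (RTD), and SAP 5.10 analyses by treatment group and overall. No split by test-dose status is planned.

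**The concern.** A change from a stable state asks whether the patient is back to normal; the best expected answer is about zero. A change from Day 1 of an exacerbation asks how far the patient has improved during the course, and a negative value is hoped for. Read literally, the baseline rule gives the first quantity to patients who had a test dose and the second to those who did not, then puts both in one RTD column. The trial has no comparator, so the baseline is the only reference for CCQ change. The share of patients test-dosed is set by a safety-committee decision and by who happens to exacerbate, neither of which says anything about response to treatment.

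**Working it through.** **The plan's own figure.** SAP 4 estimates that 30 of 150 enrolled patients will exacerbate and be treated (30/150 = 20%). It is a planning estimate without a formula, so there is no calculation to reproduce.

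**Notation.** The documents give no values for e or r.
- e = mean CCQ rise from stable state to Day 1
- r = mean CCQ at Day 7 minus stable state
- p = share of treated patients who had a test dose

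**Assumptions.** e and r are the same in both groups. The baseline-visit form precedes the test dose. The Day 1 form precedes the first home dose. Patients first dosed in Part 1 are set aside until the end.

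**Step 1: change under the literal rule.**
- Test-dosed: Day 7 minus stable = r
- Untested: Day 7 minus Day 1 = r − e
- Difference between groups: r − (r − e) = e, with no difference in clinical course

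**Step 2: pooled mean.** p·r + (1 − p)(r − e) = r − (1 − p)e.

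**Step 3: plausible p.** If only 50 of 150 are test-dosed, the expected number among 30 treated is 30 × 50/150 = 10, so p = 1/3. With equal exacerbation risk, and all 50 entering the dormant period, a hypergeometric distribution (150 patients, 50 tested, 30 treated) gives a 95% range of 6 to 15, or p = 0.20 to 0.50. If the test dose is kept for everyone, p = 1.

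**Step 4: illustration, assumed e = 1.0 and r = 0.5.**

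| Test-dosed among 30 | p | Pooled change |
|---|---|---|
| 6 | 0.20 | 0.5 − 0.80 = −0.30 |
| 10 | 0.33 | 0.5 − 0.67 = −0.17 |
| 15 | 0.50 | 0.5 − 0.50 = 0.00 |
| 20 | 0.67 | 0.5 − 0.33 = +0.17 |
| 30 | 1.00 | 0.5 − 0 = +0.50 |

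With one common reference the answer would be +0.50 (from stable) or −0.50 (from Day 1), whatever p is.

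**Step 5: range over e, with r = e/2 and p = 1/3.**

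| e | Test-dosed | Untested | Pooled |
|---|---|---|---|
| 0.5 | +0.25 | −0.25 | −0.08 |
| 1.0 | +0.50 | −0.50 | −0.17 |
| 1.5 | +0.75 | −0.75 | −0.25 |

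At p = 1/3 the pooled mean lies e/3 from the Day 1 quantity and 2e/3 from the stable-state quantity.

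**Step 6: when the sign turns.** The pooled mean is negative when r/e < 1 − p: below 0.80 at p = 0.20, 0.67 at p = 1/3 and 0.50 at p = 0.50. Over p = 0.20 to 0.50 the sign varies only for r/e between 0.50 and 0.80. Over p = 1/3 to 1 it varies only for r/e between 0 and 0.67. With full recovery (r = 0) it is never positive; with no improvement since Day 1 (r ≥ e) it is never negative.

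**Step 7: patients from Part 1.** They may enter Part 2, but their first RESP301 dose was in Part 1, where no CCQ is taken. Under the literal rule they have no baseline CCQ, and SAP 5.1 does not in general impute missing data.

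**The case against.** **The SAP rule is ambiguous.** SAP 5.1 omits the word first. Read per period, it could give every treated patient a treatment-period baseline. This stands as a description of 5.1 alone, but protocol 10.4.1 and SAP 5.5 and 5.8 all point to the first administration.

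**Day 1 timing is not visible.** If the Day 1 form follows the first home dose, untested patients also fall back to a pre-exacerbation value and the mixture largely disappears. That is correct. In that case, though, no patient has an exacerbation baseline and change over the course is not measured.

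**Redaction.** The detailed efficacy definitions in protocol 10.4.3 are blacked out and may specify the CCQ reference. This limits certainty; the finding concerns the visible rule.

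**No pooled CCQ table is planned.** A reader might infer that the SAP prescribes a pooled CCQ-change output. It does not: CCQ change is absent from SAP 3.1 and from the table list in 15.2, and 5.1 presents variables by visit. The defect arises when the protocol's endpoint is derived with the only visible rule.

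**The stable reference is defensible.** The protocol defines recovery as return to the patient's usual state. That supports reporting the stable comparison for everyone, not for some patients only.

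**Small stakes.** This is a descriptive, single-arm feasibility study with about 30 treated patients. That limits the severity but leaves the rule unsound.

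**Conclusion.** The concern holds for CCQ change. Under the visible rule the reference point depends on test-dose status. The two groups' changes differ by e for that reason alone, and the pooled mean r − (1 − p)e is not interpretable as a treatment-period change. If all patients are test-dosed there is no mixture, but every change is then measured from a stable state up to 12 months old. The result rests on the baseline-visit and Day 1 forms each preceding dosing, and on the redacted definitions not saying otherwise.

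Four stronger inferences are not supported:
- That the pooled value has no meaning. It is a weighted mix of two changes, each interpretable on its own.
- That its sign generally depends on the test-dosed share. This is so only with partial recovery, 0 < r/e < 1.
- That with e = 1.0 the result could move by a full CCQ point. That needs p = 0 at one extreme, with no treated patient test-dosed, although at least 50 enrolled patients are. From p = 1/3 to p = 1 the shift is 2e/3, or 0.67.
- That other measures, such as body temperature, are affected. No change-from-baseline endpoint for temperature is visible, and VAS is not scheduled at the baseline visit.

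The point should be corrected before analysis. It concerns a secondary efficacy endpoint and leaves the primary feasibility endpoints untouched.

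**What to change.** In SAP 5.1, define two Part 2 baselines:
- **Test-dose baseline:** last value before the test dose, for test-dose spirometry, methaemoglobin and vital signs.
- **Treatment-period baseline for CCQ:** the Day 1 form, stated to be completed before the first home dose.

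Then:
- Report CCQ change from Day 1. Report the difference from the baseline-visit CCQ separately, as return to usual state.
- Apply the same rule to test-dosed patients, untested patients and patients who came from Part 1.
- Add CCQ change to SAP 3.1 and to the table list in 15.2; changing 5.1 alone would not produce the output.
- Reconcile the dormant-period CCQ mark in SAP Table 3 with the protocol.

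The cost is SAP wording, one derived variable and a table entry. The baseline-visit and Day 1 forms are already scheduled, so no new assessment is needed. If Day 1 forms have already been collected, their completion times relative to the first home dose should be checked and reported.

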	
Part 2: Expansion Phase
 
A test dose of RESP301 at RTD will be administered during the baseline visit under clinical supervision in a minimum of 50 patients. Patients who tolerate the test dose will progress to the Dormant Period to which a further 100 participants will also be recruited with or without a test dose (depending on review of safety data after the first 50 patients). Participants in the Dormant Period will inform the clinical team if symptoms develop indicative of a possible respiratory infection (exacerbation) and will then progress to the Treatment Period, in which eligible participants receive RESP301 by courier or at a subsequent clinic visit for treatment by self-administration at home. During the Treatment Period, RESP301 is taken at the RTD three times a day at least 4 hours apart for 7 days alongside normal Standard of Care (SOC) (treatment period may extend into Day 8 depending on time of commencing on Day 1). During the Treatment Period participants may use rescue medication as required.

Comparator	Not applicable
Study design	
This is a single arm, non-randomised, open-label study.
 
Part 1(a): Dose Finding Phase
 
Up to 48 eligible participants will be administered single ascending doses of RESP301 under clinical supervision to determine the MTD, according to the following schedule:
 

• 8 participants to receive RESP301 at a dose of 1 ml

• 8 participants to receive RESP301 at a dose of 2 ml

• 8 participants to receive RESP301 at a dose of 3 ml

• 8 participants to receive RESP301 at a dose of 4 ml

• 8 participants to receive RESP301 at a dose of 5 ml

• 8 participants to receive RESP301 at a dose of 6 ml

 
Safety data will be reviewed by the PIs and Sponsor after each dose before proceeding to the next higher dose.
 
Safety data will include:
 

• Treatment-related Adverses Events including troublesome cough, chest pain or tightness, bronchospasm or dyspnoea the patients finds intolerable

• Changes in FEV1

• Changes in methaemoglobin level

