### **Treatment period**

A patient entered into the dormant period who experiences exacerbation symptoms for at least [REDACTED] will be eligible to enter the Treatment period. Patients will be instructed to contact the study team as soon as practicable to allow a study interaction to be undertaken remotely (via video link, if possible), within [REDACTED] of onset of at least one of the following:

- Fever (>38.0°C),
- Systemic malaise,
- Increased cough or wheeze,
- Increased sputum volume or increased purulence.

During the remote visit the patient's symptoms will be discussed and if the patient is willing to continue in the study, [REDACTED]

Note that if COVID-19 is suspected, the patient will be advised to follow the prevailing NHS guidance on testing for COVID-19 taking into account any specific recommendations for patients with COPD or bronchiectasis. Where serial SARS-CoV-2 swabs are undertaken, data will be collected for analysis.

During the treatment period, [REDACTED], at home/ community setting, patients will be asked to:

- Administer RESP301 [REDACTED] at the dose determined in Part 1 of the study (RTD).
- Take daily temperature measurements
- Complete a daily diary to record treatment doses

- Attend a daily call with study coordinator to check compliance, assist with issues with product, and report any AEs and changes to medications or medical history, including COVID-19 test results, if available.

[REDACTED]

[figure not shown]
[REDACTED]

[REDACTED]

In summary, the Part 2 of the study will involve the following visits/calls and study phases:

- Screening/Baseline Visit (Day 0), including test dose if required
- Dormant period (from Day 1, until the first exacerbation or end of study at week 52)
  - During this phase, monthly calls will be conducted
- Remote study visit ([REDACTED])
- Treatment period ([REDACTED])
  - During this phase, daily monitoring calls will be conducted; additionally, a call to collect [REDACTED] data will be conducted 1 day PEoT
- Follow-up period ([REDACTED])
  - Patients who still experience exacerbations symptoms at the end of the [REDACTED] treatment period will be asked to continue the study diary until symptoms return to baseline level (i.e. VAS score = 0), or until [REDACTED] after the end of treatment, whichever is sooner.
  - All patients will receive a follow-up call [REDACTED]
  - All patients will receive a final follow-up call [REDACTED]

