## **5.10 Analysis of Efficacy Variables**

All primary and secondary efficacy parameters, see section 3, will be summarized descriptively and no formal statistical analyses will be performed. The analyses will be performed by treatment group and overall, for both the FAS and PPS set using appropriate descriptive statistics. The results of the spirometry will also be presented over time, i.e. baseline, 30-, 60- and 90-minutes post baseline.

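### Time to recovery is cut off by the end of the VAS diary, and the SAP neither lists the endpoint nor says how patients still unrecovered at that point are handled

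*SAP*

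**What the plan says.** **Endpoint.** The secondary endpoints in the protocol synopsis (section 1) include "time to recovery (days until patient feels all their symptoms are back to their usual baseline (all VAS = 0". The same list has the percentage recovered by Day 7 and by Day 14 after starting treatment.

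**When recording stops.** SAP Table 3, footnote 7, sets VAS recording as "Daily during the treatment period, and if not recovered by end of treatment, continued until recovery or Day 14 post end of treatment". Protocol 5.1 (Treatment period) has the same rule: the diary continues "until symptoms return to baseline level (i.e. VAS score = 0), or until" a time that is redacted. Treatment lasts 7 days, and the synopsis adds that the "treatment period may extend into Day 8 depending on time of commencing on Day 1".

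**How data are summarised.** SAP 5.1 applies one set of descriptive statistics (count, mean, SD, range, median) to all recorded and derived continuous variables. On missing data it says: "In general, missing data will be treated as missing and no attempts will be made to impute values for missing data". Protocol 10.4.1 is similar: "In general, missing values will not be replaced unless otherwise stated". SAP 5.10 says the efficacy parameters of SAP section 3 "will be summarized descriptively and no formal statistical analyses will be performed".

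**What is absent.** The only secondary endpoint in SAP 3.1 is tolerability of the test dose. Time to recovery is not named there, in SAP 5.10, or in the efficacy table list (SAP 15.2). VAS scores are summarised by time point only (SAP 5.11). No visible text mentions Kaplan-Meier, a censoring day, or a value for a patient who has not recovered.

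**The concern.** A patient whose symptoms have not settled when the diary ends has no recovery time, only the knowledge that it exceeds about 21 days. That is a right-censored observation. The visible SAP defaults suit complete measurements: they have no way to express a time longer than the limit, and they leave blanks blank. A programmer with only those defaults would most naturally compute the mean and median among patients who recovered.

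That summary is conditional on recovery, and it responds weakly to how slow recovery really is. The slower the recovery, the more of the slow patients fall out of it. Collecting preliminary efficacy data is a stated secondary objective, and there is no control arm against which an over-short recovery time would stand out.

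**Working it through.** The documents give no expected recovery time, no expected share unrecovered and no formal sample-size calculation, so there is no plan figure to reproduce. The check has two parts.

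**1. Is the endpoint censored by design?**
- Treatment 7 days + 14 days = Day 21. If treatment runs into Day 8, 8 + 14 = Day 22.
- A patient with any VAS above zero on that day has no recorded recovery day. So yes.

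**2. What do the defaults give if such patients are left out?**

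Inputs from the documents: limit C = 21 days (22 as a check) and about 30 treated patients (SAP section 4). Assumed inputs: true median m of 5, 7, 10 or 14 days, and a Weibull recovery distribution with shape k (k = 1 is exponential).

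- Share unrecovered at C: S = 2^(−(C/m)^k).
- The recovered-only median x solves 1 − 2^(−(x/m)^k) = (1 − S)/2, so x = m × [−log2((1 + S)/2)]^(1/k).

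Example, exponential, m = 10, C = 21: S = 2^(−2.1) = 0.233. Then (1 + 0.233)/2 = 0.617, −log2(0.617) = 0.698, and x = 10 × 0.698 = 7.0 days. Expected unrecovered: 30 × 0.233 = 7.0 patients.

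Exponential, C = 21:

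| True median (days) | Unrecovered | Of 30 | Recovered-only median | Shortfall |
|---|---|---|---|---|
| 5 | 5.4% | 1.6 | 4.6 | 0.4 |
| 7 | 12.5% | 3.8 | 5.8 | 1.2 |
| 10 | 23.3% | 7.0 | 7.0 | 3.0 |
| 14 | 35.4% | 10.6 | 7.9 | 6.1 |

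A Kaplan-Meier estimate censored at Day 21 targets the first column as long as more than half recover by then.

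**Sensitivity to shape.** The same formulas with k = 1.5 and C = 21:

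| True median (days) | Unrecovered | Recovered-only median | Shortfall |
|---|---|---|---|
| 5 | 0.3% | 5.0 | under 0.1 |
| 7 | 2.7% | 6.8 | 0.2 |
| 10 | 12.1% | 8.9 | 1.1 |
| 14 | 28.0% | 10.4 | 3.6 |

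**Sensitivity to the limit.** With C = 22, exponential, m = 10: S = 2^(−2.2) = 0.218, 6.5 of 30 unrecovered, recovered-only median 7.2 days. Little changes.

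**Means.** The fair comparator is the mean restricted to the 21-day window, (1 − S) × m / ln 2 in the exponential case. For m = 10 that is 0.767 × 14.43 = 11.1 days. The recovered-only mean is (11.06 − 21 × 0.233)/0.767 = 8.0 days. The unrestricted mean of 14.4 days includes time after the diary ends, which Kaplan-Meier cannot estimate either.

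**Small-sample check.** In 4,000 simulated trials of 30 patients (exponential, m = 10, whole-day times, limit Day 21), the recovered-only median averaged 7.5 days and the typical Kaplan-Meier median was 11 days. Rounding up to whole days lifts both.

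**The case against.** A reader might infer that the SAP prescribes a mean and median among recovered patients and that the reported figure will therefore be wrong. The documents do not support that.

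- **No analysis is stated.** SAP 5.10 covers the parameters of SAP section 3, and time to recovery is not one of them. The 5.1 rules are defaults, and both missing-data sentences open with a general qualifier that allows exceptions.
- **Not recovered is not the same as missing.** A patient with VAS above zero at the limit has been observed. No text says that such a patient is coded missing rather than censored or given the limit day.
- **Nothing says that hospitalisation ends the record.** It would be wrong to assume that a patient admitted during treatment has no recovery time. Protocol 8.5 has symptoms recorded at follow-up.
- **Redaction.** The efficacy text in protocol 10.4.3 is blacked out, so a rule there cannot be ruled out.
- **Other outputs give partial protection.** The default table prints the sample size, VAS scores are tabulated and listed, and the protocol has recovery percentages at Day 7 and Day 14.
- **The size is assumed, and the endpoint is secondary** and descriptive, in a single-arm feasibility study.

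All of this stands, and it limits the point to a gap. It does not close the gap. Protocol 10.4 refers further detail to the SAP, which has no rule. Adding the endpoint without one would still leave only the defaults. Printing the sample size shows that patients are absent but does not correct the median. The Day 7 and Day 14 percentages help only if non-recovered patients stay in the denominator, which is also unstated. Assigning the limit day to non-recovered patients would give the right median when more than half recover, but the mean would then be a restricted mean and would have to be labelled so.

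**Conclusion.** The concern holds as a gap in the SAP, with a predictable direction of error if the gap is filled by default. The endpoint is in the protocol, recording stops at about Day 21 or 22, and no visible text lists the endpoint in the SAP or says what happens to patients unrecovered by then. If they were left out under SAP 5.1, recovery time would be understated: the recovered-only mean would be too short and the median could not come out longer than the true one.

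The size depends on the share unrecovered, which the documents do not give. For assumed true medians of 5 to 7 days the shortfall in the median is about 0.4 to 1.2 days under exponential recovery and at most about 0.2 days under Weibull shape 1.5. At 10 days it is about 3.0 and 1.1 days, and at 14 days about 6.1 and 3.6 days. So it may be negligible if recovery is quick and material if a fifth or more are unrecovered. The change is worth making before database lock, in proportion to a secondary descriptive endpoint.

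**What to change.** In SAP 3.1 and 5.10:

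1. List time to recovery as a secondary efficacy endpoint, with recovery defined as in the protocol (all VAS = 0) and the clock starting at the first treatment-period dose, not the baseline test dose.
2. Report the Kaplan-Meier median with the number censored. Censor patients who have not recovered at their last VAS or diary day.
3. Keep patients who die, or who are hospitalised with no later recorded recovery, as not recovered to the end of the diary window.
4. If Kaplan-Meier is not wanted, report the median with non-recovered patients ranked last and shown as beyond the end of the diary.
5. Report recovery by Day 7 and by Day 14 with all patients treated in the treatment period in the denominator.

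Add the output to the table list in SAP 15.2. The cost is SAP wording and one table. No new data are needed, because VAS is already recorded daily up to the limit.
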